## **MRI Scans**

**MRS acquisition and processing:** All images will be acquired using a Siemens 3 Prisma 3T scanner (Siemens Medical Solutions, Malvern, PA, USA) equipped with a maximum gradient strength of 80 mT/m and a rise time of 200 µs, which will provide nearly double the signal-to-noise ratio enabling high-resolution structural imaging data. The new digital RF system equipped with 64-channel RF head-and-neck coil and the two-channel RF excitation coils will provide better spectral resolution with improved signal-to-noise ratio while at the same time providing more uniform excitation pulses. For image guidance and MRS volume of interest prescription, anatomic images will be obtained using a T1-weighted MPRAGE sequence with the following parameters: TR/TI/TE =2300/900/3.02 msec; flip angle=8°; FOV read=256 mm; matrix=256; slice thickness=1 mm; GRAPPA factor of 0; total scan time=10 minutes.

**Single Voxel MRS Acquisition:** Single Voxel Spectroscopy (SVS) is used to quantitate neurometabolites of interest in target brain regions. The scanning protocol and post-processing methodology will be used in accordance with previously published reports,[24, 27] but modified for the Prisma 3T platform. SVS will be acquired using Chemical Shift Selective (CHESS)-based MRS sequence using settings of TR/TE = 3000/30 ms, sampling size=128 averages, bandwidth=1048Hz with sampling size = 1024, 128 averages. Two voxels with size of 17 x 30 x 17 mm^3 located in the left and right basal ganglia will be used for SVS. Spatial localization will be implemented using PRESS technique.[59] Numerically optimized Shinnar-Le Roux (SLR)

radio frequency pulses will be used for PRESS (90°, 180°, 180°) and CHESS (90°, 90°, 90°).[60] Four unsuppressed water FIDs (free induction decay) will be also acquired for eddy current and phase correction[61] and to compute metabolite/water ratios if needed (LC Model). The FWHM of the unsuppressed water peak will be optimized to <14 Hz by shimming. The spectral data will not be apodized.

**Chemical Shift Imaging (CSI):** The application of a single voxel to a specific region limits evaluation of diffuse or global cortical and subcortical glutamate abnormalities that may occur in association with inflammation and have been proposed to occur in unipolar depression.[62] Simultaneous sampling from multiple voxels placed bilaterally on the basal ganglia gray matter, white matter and adjacent neocortical regions will provide a more expansive evaluation of relevant brain structures that have been implicated in the impact of inflammatory cytokines on behavior. CSI will be acquired using 2D Point Resolved Spectroscopy (PRESS)-based MRSI sequence using settings of TR=1590 ms, TE=30 ms, averages= 7, matrix=16×16, voxel size=11.3×11.3×15 mm^3, slice thickness=15mm. The raw files will be processed using LC Model package-Version 6.2-2b.[63]

Post Processing:

**Metabolite Spectral Fitting:** The LC Model is an operator-independent commercial software package that fits in vivo metabolite spectra using model resonances acquired from multiple compounds in standard phantom solutions. The water suppressed time-domain data will be analyzed between 1.0 ppm and 4.0 ppm without T1 and T2 correction. The basis set provided by the vendor of the LC Model[63] will be used and then scaled to account for receiver gain differences. While the entire 18 metabolite basis set would be entered during metabolite fitting, the analysis will only include metabolite variances (Cramer Rao Lower Bounds or CRLB) <25. Use of a high field strength (Prisma 3T) scanner and short TE (=30 msec) sequence has enabled us to calculate Glu/Cr with high reliability and very low metabolite variance (CRLB <10) during our previously published MRS studies.[24, 27]

**Water scaling and relaxometry:** The post processing pipeline has been developed to yield absolute quantitation, metabolite/water and metabolite/creatine values. LC model provides an automated water scaling settings which will be used (DOWS). All data (water signal and water suppressed data) will be phased followed by quantification of water relaxometry data. The relaxometry data will then be fitted to obtain water reference data and in the case of gray matter following segregation of the CSF and tissue water constituent. Finally, water signal will be scaled to that of the resulting value obtained in previous steps. The water scaling portion of the post processing will be done as soon as data is acquired.

Tissue correction and segmentation: T1-weighted images will be segmented into gray matter (GM), white matter (WM), and cerebrospinal fluid (CSF) compartments using FreeSurfer (<https://surfer.nmr.mgh.harvard.edu/fswiki>) on the whole brain T1 images. A volume of interest (VOI) will be generated on the T1 images, matching the location and size of MRS voxel. Volumes of GM, WM and CSF segments in this volume-of-interest will then be generated using FreeSurfer. The absolute metabolite concentrations generated by the LCModel will then be corrected for CSF using the formula  $C = C_o \times 1/(1-f_{CSF})$ , where C is corrected metabolite concentrations, Co is metabolite concentrations generated by LCModel output and fCSF is fraction of CSF volume.[64, 65] The final output of the absolute metabolite quantitation will be provided in units of molality. Absolute quantitation using CSI data is challenged by multiple methodological problems[66] and often requires customized automated programs to correct for atrophic tissue changes, B0 field inhomogeneity distortions, and water suppression in each subvoxel may be less than optimal. Consequently, CSI data will be assessed using metabolite values normalized to creatine. This will be accomplished after ensuring that raw uncorrected concentrations of creatine (Cr) and phosphocreatine (PCr) are not significantly

different among the different study groups in the prescribed region of interest. An exploratory analysis of the impact of inflammation on other metabolites of interest including choline (Cho), myoinositol (InS) and n-acetyl aspartate (NAA) will also be conducted.

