Thus, CNS glutamate may serve as a final common pathway to CNS pathology and behavioral and cognitive disturbances in breast cancer patients after treatment. Interestingly, memantine, a drug that antagonizes glutamate signaling was found to preserve cognition in cancer patients undergoing whole brain radiotherapy, indicating that blocking glutamate may have neuroprotective effects under conditions of an increased inflammatory load. Taken together, these data suggest that glutamate may be an outstanding target for reversing the behavioral pathology associated with inflammation during breast cancer and its treatment. Demonstration that targeting glutamate to reverse fatigue and cognitive changes in patients with high inflammation and could potentially help treat the long-term toxicities of breast cancer and its treatment. The goal of the current proposal is to test the hypothesis that reduction of glutamate in breast cancer survivors with fatigue and high inflammation will be associated with decreased CNS glutamate and decreased symptoms of fatigue and cognitive function including anhedonia and psychomotor slowing. To test these hypotheses the following aims are proposed:

**Aim 1: To study the impact of 8 weeks of riluzole treatment on CNS glutamate concentrations in breast cancer patients with increased fatigue and high inflammation.**

Using a double-blind randomized controlled trial design, 40 female breast cancer patients with increased fatigue ( $\geq 4$  on a 10 point scale) and high inflammation (CRP $>3$ mg/L) will be treated for 8 weeks with either riluzole or placebo (n=20 per group). At baseline and at 1 and 8 weeks of treatment, all subjects will undergo single voxel MRS to measure CNS glutamate. Voxels will be placed in the right and left basal ganglia and the dACC. In addition, chemical shift MRS imaging will be employed to explore potential glutamate changes in other brain regions of interest.

**Hypothesis 1:** Breast cancer patients administered riluzole will exhibit greater decreases in basal ganglia and dACC glutamate compared to women treated with placebo.

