**Riluzole Flowchart:**

### **Randomization**

Subjects will be randomized to 100 mg of riluzole (50 mg po BID) or an identical appearing placebo in a 1:1 fashion with no stratification. Subjects will be instructed to take the study medication on an empty stomach (1 hour before or 2 hours after meals). The dosage of riluzole is based on several clinical trials that have previously used this medication to treat a number of psychiatric disorders ranging from depression to generalized anxiety disorder as well as ALS.[31] A randomly generated sequence of assignments to riluzole or placebo will be created and maintained by the study pharmacist. Subjects will be randomized in blocks of 4. If a subject drops out prior to receiving the first dose of medication, she will not be included in data analyses and her randomization assignment will “roll over” to the next recruited subject until 40 subjects have received at least one dose of medication or placebo.

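### A non-significant creatine difference with 20 women per arm does not show that creatine is comparable, so it cannot license reading exploratory CSI Glu/Cr results as glutamate effects

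*Combined protocol and SAP*

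**What the plan says.** Section 6, MRI Scans, in the paragraph on tissue correction and segmentation, explains that absolute quantitation from CSI faces several methodological problems. It then concludes: "Consequently, CSI data will be assessed using metabolite values normalized to creatine". The condition is that "raw uncorrected concentrations of creatine (Cr) and phosphocreatine (PCr) are not significantly" "different among the different study groups in the prescribed region of interest". The protocol's verb for this step is ensuring, so a non-significant result is treated as settling the matter. The paragraph states no test, significance level, visit, equivalence margin or confidence interval, and no alternative if the check fails.

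The role of CSI is limited. In Section 5, Aim 1, "chemical shift MRS imaging will be employed to explore potential glutamate changes in other brain regions of interest"; the target regions of that aim are measured by single-voxel MRS. Aim 2 also labels its CSI analysis exploratory, and Section 10 describes no CSI analysis. Section 5 sets 20 women per group, and the Randomization section allocates "in a 1:1 fashion with no stratification".

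**The concern.** A non-significant test says only that the data do not exclude zero. It does not say that the difference is small, and with 20 per arm the range of differences it leaves open is wide.

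Timing matters as well. In a randomised trial, a baseline comparison of creatine can only pick up chance imbalance. What would mislead is a drug effect on creatine between Baseline 1 and Weeks 1 or 8, because it moves the denominator of Glu/Cr in one arm. The plan does not say that the check looks there.

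At stake is the wording of the exploratory CSI conclusions. After a passed check, a change in Glu/Cr would be reported as a change in glutamate, although the check had not ruled out creatine as its source.

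**Working it through.** The plan gives no figure of its own for this check, so there is none to reproduce. The d = 0.5 in Section 11 belongs to basal ganglia glutamate under Aim 1. Whether that figure is right is a separate matter, and it is not used as a yardstick here.

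**Inputs.** n = 20 per arm (Section 5, Aim 1). Assumed, because the plan is silent: a two-sample t test, two-sided alpha 0.05, one test. Differences are in SD units of the creatine measure compared.

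**Largest observed difference that passes.** t(0.975, 38) × √(2/20) = 2.024 × 0.316 = 0.64 SD.

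**Example.** An observed difference of 0.5 SD gives t = 0.5 × √(20/2) = 1.58 and p = 0.12. The 95% CI is 0.5 ± 0.64, that is -0.14 to 1.14 SD. The check passes, yet the interval includes differences above one SD.

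**Probability of passing for a given true difference** (1 minus noncentral-t power):

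- 0.25 SD: 0.88
- 0.5 SD: 1 - 0.338 = 0.66
- 0.75 SD: 0.36
- 0.9 SD: 0.21

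**Sensitivity, true difference 0.5 SD:**

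- 16 per arm (the dropout figure in Section 6, Participants, read as 20% of 40 dosed): cut-off 0.72 SD, pass probability 0.72.
- Alpha 0.10: 0.54.
- Baseline-adjusted comparison, which is not planned for this check: 0.57, 0.42 and 0.27 at correlations 0.5, 0.7 and 0.8.
- Cr and PCr both shifted by 0.5 SD, tested separately and treated as independent: both pass with probability 0.66 × 0.66 = 0.44.

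**How a creatine shift reaches the ratio.** Let Δ be the arm difference in change. On the log scale, Δ(Glu/Cr) = Δ(Glu) - Δ(Cr). Anything that multiplies both metabolites alike cancels. The CSF correction given in the same section, 1/(1 - f_CSF), is such a factor. Only the creatine-specific part of a shift reaches Glu/Cr.

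**Would an equivalence test do instead?** Two one-sided tests at 5% each, with a margin of ±0.5 SD and a true difference of zero, need 69 per arm for 80% power. With 20 per arm the power is about 3%, and the smallest margin reaching 80% is about 0.95 SD. The trial cannot show equivalence within 0.5 SD, so estimation is the practical route.

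**The case against.** The best case against the point is that CSI is exploratory, randomisation is in place, and a light check on creatine is adequate for its purpose. Much of this stands, and it rules out several stronger readings.

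- A reader might infer that the check lets through creatine shifts as large as the effect the trial seeks. The documents do not support that comparison: d = 0.5 is for the Aim 1 outcome, and no effect size is stated for CSI. Equal SD units also need not mean equal percentages. Suppose creatine has a CV of 5 to 15% and glutamate 8 to 15% (assumed; the documents give none). A creatine shift equal in percentage to 0.5 SD of glutamate would then pass with a probability anywhere from below 0.01 to 0.87.
- A reader might infer that a raw creatine difference carries over in full to Glu/Cr. It does not where the cause is CSF fraction or signal scaling shared with glutamate. How much is shared is unknown.
- A reader might count chance differences in creatine as bias. Under randomisation they are already part of the sampling error of Glu/Cr. Only a true treatment effect on creatine biases attribution; the documents neither report nor exclude one.
- The 0.64 SD is not a fixed percentage. If the check were made on change scores, the SD of change is √(2(1 - r)) times the cross-sectional SD. At an assumed r = 0.8 the cut-off is 0.64 × 0.63 = 0.40 cross-sectional SD.
- A water-scaled analysis is not an obvious remedy. The pipeline is said to "yield absolute quantitation, metabolite/water and metabolite/creatine values", but unsuppressed water acquisition is described only for single-voxel MRS, and the protocol itself distrusts absolute CSI values.

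None of this makes a non-significant result evidence of comparability, or tells the reader at which visit creatine is compared.

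**Conclusion.** The point holds as a minor one, confined to the exploratory CSI analyses. The stated rule cannot support the conclusion drawn from it: with 20 per arm it passes any observed creatine difference below 0.64 SD, and a true 0.5 SD difference about two times in three. Those figures assume a single two-sided test at 0.05. If both Cr and PCr shift and are tested separately, the pass probability falls, to 0.44 under independence. The logical fault does not depend on these assumptions.

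The documents do not allow a figure for the resulting distortion in Glu/Cr. It depends on CVs they do not report and on how much of any creatine shift glutamate shares. Nor do they support a reading that the primary result is compromised. For single-voxel data the protocol describes CSF-corrected absolute quantitation, and the creatine check is not attached to it. Section 10 says only glutamate, without naming a scale; the caution would extend to Aim 1 only if that outcome were also analysed as Glu/Cr.

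**What to change.** In the tissue correction and segmentation paragraph, before unblinding:

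1. Remove the significance condition on Cr and PCr.
2. For each CSI region, estimate the arm difference in change of the creatine quantity used as denominator, from Baseline 1 to Week 1 and to Week 8. Report it with its 95% CI beside the matching Glu/Cr result.
3. Describe CSI effects as effects on Glu/Cr. Do not call them glutamate-specific where the creatine interval allows a change that could account for the Glu/Cr difference.
4. Optionally, add a water-scaled CSI sensitivity analysis, but only if unsuppressed water data exist for CSI. Agreement between the two should not be a required rule.

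No new patients, scans or visits are needed. The cost is a little more analysis and a more cautious exploratory conclusion. With 20 per arm the creatine interval has a half-width of about 0.64 SD (of change), so many CSI findings will have to stay at the level of Glu/Cr. Raw creatine also includes scaling shifts that cancel in the ratio, so the interval errs towards caution.

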### **Management of MRS Incidental Findings**

The purpose of these scans is not to make a clinical determination of patients' brain health. However, if any incidental finding is noticed during the scan, the information will be provided to patients or their medical provider-of-record for further management. Incidental findings are those abnormalities seen in patients' brain images during the scanning process, which may or may not be of clinical importance. Follow-up of the scan findings will be the responsibility of the patients' Emory Healthcare provider-of-record.

### **7. Data Quality Monitoring Plan:**

Periodic chart monitoring will be conducted by study personnel to validate integrity of the data. Chart reviews will take place after each block of five subjects and may include, but not be limited to, the presence of a signed informed consent document, documentation that the informed consent was obtained prior to performance of any study-related evaluations, documentation related to billing compliance, treatment calendars, enrollment reported to OCR, enrollment recorded in Oncore ®, treatment order and/or prescription form copies, and source documentation as defined in the Winship Clinical Trials Office's Standard Operating Procedure.

The project will be subject to random chart audits conducted by the Winship Clinical Trials Office in accordance with Standard Operating Procedures. A minimum of 5 subject charts may be randomly audited as requested by the PI, the Associate Director for Clinical Research, the Director of the CTO, the IRB, the ORC, or other Emory research compliance personnel, or the assistant director on an as needed basis.

1. Any of the above persons may request a random audit of clinical trials records for the subjects enrolled on any study managed by this office.
2. When records are requested they will be made available to the person listed above within 2 hours.
3. Chart review may include, but not be limited to, the presence of a signed informed consent document, documentation that the informed consent was obtained prior to performance of any study-related evaluations, documentation related to billing compliance, treatment calendars, enrollment reported to OCR, enrollment recorded in Oncore ®, treatment order and/or prescription form copies, and source documentation.
4. Audit will be performed by the persons listed above in "Procedure" or the internal monitors.
5. Audit results may be reviewed by the Winship CTO Director, the Assistant Director of Regulatory/Compliance, the Assistant Director for Clinical Research and the Office of Research Compliance. Significant findings will be discussed with the nurse, coordinator, principal investigator, and Director.
6. Deficiencies will be corrected within five working days and presented to the Assistant Director for review at that time. A corrective and preventive action plan will be developed as indicated by the audit results.

### **Quality Improvement**

Charts with significant deviations from Winship CTO policy will indicate the need for further audit of records belonging to the involved nurse or coordinator. Limited findings of noncompliance will signal a need for increased education and/or quality monitoring. Significant noncompliance can lead to disciplinary action.

Failure to comply with this policy may be grounds for discipline by the University. Any disciplinary action taken by the University will follow the rules governing the individual's employment category.

### **8. Sources of Materials:**

Research materials to be obtained will include clinician-administered psychiatric assessments, neurocognitive assessments, self-report questionnaires, blood sampling, MRS scans, physiological variables, and saliva sampling. Material for evaluating baseline medical status will be obtained from blood, urine, patient report and their medical record when available. Data to be recorded from subjects will include standardized ratings of fatigue, depression and cognitive function, as well as clinical information derived from medical records regarding tumor, patient, and treatment characteristics. Data to be obtained from peripheral blood will include complete metabolic panel; CBC with differential; hCG quantitative serum; plasma concentrations of cytokines and their soluble receptors, gene expression, gene polymorphisms, exosome, and/or hormonal analysis. Data obtained from urine will include urinalysis and toxicology screen. Data obtained from saliva will be used to assess hormone levels and DNA methylation changes at time of study visit. Clinical data will be used to assess eligibility and safety and will be collected via interview and documented by study clinicians. Standardized clinician-administered and self-report assessments will be administered and collected by study physicians or his designees. Blood will be obtained in the clinic laboratories by trained phlebotomists, and the samples will be collected and processed by study personnel.

All data, including questionnaires and blood will be coded by unique identifying numbers. Subjects' names will not be linked to their biological samples or clinical data in REDCap. Subject name and identifying number will be kept in a casebook in a locked cabinet and/or office. Only IRB qualified research staff and study physicians will have access to subject identifiers. Research personnel analyzing blood or clinical data will not be provided information from which they could identify subjects. All information will be obtained solely to determine eligibility for study participation or for research purposes. Nevertheless, any significant abnormalities uncovered will be reported to the subject and his/her treating physician for follow-up or will be used by study clinicians to determine appropriate medical care and/or study termination in the case of adverse event

### **9. Data Collection and Management:**

The data management team will use REDCap.[67] REDCap allows database construction, an interface for collecting data, data validation, and automated export procedures for data downloads to statistical packages (SPSS, SAS, Stata, R). Scales will be completed securely via the internet via standard web access. Research staff will enter scale responses directly into the REDCap electronic assessment forms. Electronic assessments will be completed on computer terminals under supervision of study staff. [name] is currently using REDCap for 2 of his funded projects, and he and his staff have extensive experience with its usage. Data will be stored indefinitely in a secure location until no longer needed by investigator.

